### **B.7.5. ADDITIONAL DATA COLLECTION**

The following will also be collected:

- Comparison of mean change from Baseline in upper limb pain mean VAS score evaluated at 1, 3, 6 & 12months after device activation.
- Subject Satisfaction, evaluated at 3, 6 & 12months after device activation.
- Patient Global Impression of Change, evaluated at 3, 6 & 12 months after device activation.
- Quality of paresthesia at 3, 6 & 12 months.
- Comparison of mean change from baseline in other pain mean VAS score evaluated at 3, 6 & 12- months after device activation (if available)
- Activity level based on Intellis™ Adaptive-Stim data log.

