### **B.3.2. INCLUSION CRITERIA**

In order to participate in the study, a subject must **MEET ALL** of the following inclusion criteria:

1. Be diagnosed with chronic, intractable pain of the upper limbs related to the cervical spine and/or neuropathic arm pain.
2. Be a candidate for SCS system (trial and implant) per labeled indication (upper limb pain due to one of the conditions listed in indications statement)
3. Considering daily activity and rest, has average upper limb pain intensity of  $\geq 5$  out of 10 cm on the Visual Analog Scale (VAS) at enrollment
4. Be willing and capable of giving written informed consent to participate in this clinical study based on voluntary agreement after a thorough explanation of the subject's participation has been provided.
5. Be willing and capable of subjective evaluation, read and understand written questionnaires, and read, understand and sign the written informed consent.
6. Be 18 years of age or older at the time of enrollment
7. Be on a stable pain medication regime, as determined by the study Investigator, for at least 30 days prior to enrolling in this study
8. Be willing and able to comply with study-related requirements, procedures, and visits, including not increasing pain medications through the three months visit
9. Has adequate cognitive ability to use a patient programmer and recharger as determined by the Investigator

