#### **B.5.4.1 SAMPLE SIZE RATIONALE**

There is no statistical hypothesis to be evaluated in this study. It is believed that approximately 45 subjects permanently implanted subjects will be sufficient to evaluate the effectiveness and to collect additional safety data of the DTM SCS programming in the target population at the primary endpoint.

Up to 90 subjects will be consented to participate in the eligibility screening process. Those who do not meet all the inclusion criteria and none of the exclusion criteria will be considered screen failures and will not move into the trialing phase. It is estimated that approximately 55 subjects will be trialed. Only subjects with a successful trial phase will be eligible to move into permanent implantation of the device.

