### **B.6.13. 6 MONTHS AFTER DEVICE ACTIVATION ( $\pm$ 31 DAYS)**

. The 6 Months visit will consist of the same assessments as the 3-month visit except the anterior-posterior (AP) and lateral X-ray imaging is optional. Subjects will visit the study site where they will be assessed for pain, extent of disability, quality of life, Patient Global

Impression of Change, and subject satisfaction. Paresthesia generated by the stimulator will be assessed. Programming adjustments may be made, as needed. Subjects will also be assessed for possible adverse events and medication usage. In situations where there is an ongoing study related adverse event, subjects will be followed until resolution of that adverse event or determination that the subject's condition is stable.

However, all subjects who remain implanted at the time of Study Completion will be offered to return for an additional visit 12-months after device activation.

Following the last scheduled study visit, subjects will be followed by their pain physician at regular intervals, as dictated by standard of care at each site, in order to facilitate pain management, stimulation adjustments, possible revisions and/or replacements of neurostimulation components. Any additional non-study related monitoring of the subject will be the responsibility of the subject's personal physician, as dictated by reasonable medical care.

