#### **B.6.14. 12 MONTHS AFTER DEVICE ACTIVATION ( $\pm$ 31 DAYS)**

Subjects will be offered an optional visit at 12 months after device activation. This visit will consist of the same assessments as the 6-month visit. Subjects will visit the study site where they will be assessed for pain, extent of disability, quality of life, Patient Global Impression of Change, and subject satisfaction. Paresthesia generated by the stimulator will be assessed. Programming adjustments may be made, as needed. Subjects will also be assessed for possible adverse events and medication usage. In situations where there is an ongoing study related adverse event, subjects will be followed until resolution of that adverse event or determination that the subject's condition is stable.

Following the last scheduled study visit, subjects will be followed by the Investigator at regular intervals, as dictated by standard of care at each site, in order to facilitate pain management, stimulation adjustments, possible revisions and/or replacements of neurostimulation components. Any additional non-study related monitoring of the subject will be the responsibility of the subject's personal physician, as dictated by reasonable medical care.

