### **B.9.2. STATISTICAL ANALYSIS**

There are no formal hypotheses evaluated in this study. All baseline and outcome data will be reported using summary statistical methods. Descriptive statistics will be used to summarize baseline and outcome data collected during the study. Continuous variables will be summarized using means, standard deviations, and ranges. Categorical variables will be summarized in frequency distributions.

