**Table 1. Schedule of Study Activities**

Activity	Pre-Trial Phase		Trial Phase		Permanent Phase					12 months visit (±31 days after activation)
	Enrollment	Baseline	Start Trial Phase	End Trial Phase (up to 10 days after trial starts)	Permanent Implant (up to 60 days after end of trial)	Device Activation (0-14 days after implant)	1-month visit (±15 days after activation)	3 months visit (±21 days after activation)	6 months visit (±31 days after activation)	
Informed Consent	X									X b)
Pain Intensity Evaluation (VAS)	X			X			X	X	X	X
Medication Use	X	X	X	X	X	X	X	X	X	X
Medical/Surgical History	X	X								
Eligibility Criteria Evaluation	X									
Pain Disability Questionnaire		X							X	X
AP/Lateral x-ray imaging			X	[X]	X	[X]	[X]	X	[X]	[X]
Paresthesia Questionnaire								X	X	X
Patient Global Impression of Change								X	X	X
Subject Satisfaction								X	X	X
Adverse Event Monitoring		X	X	X	X	X	X	X	X	X
Device Programming			X			X	[X]	[X]	[X]	[X]
Device Programming Log				[X]			[X]	[X]	[X]	[X]
Study Completion				X a)				[X] c	[X] c	X c

[X] Optional activity.

a) For subjects that do not have a successful Trial Phase.

b) Some subjects may need to be reconsented to complete these visits.

c) Some subjects were originally consented to complete the study at the 3 or 6 month visit and may not consent for additional visit.

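### The comparison of mean VAS change across 1, 3, 6 and 12 months is likely, though not certain, to overstate lasting relief at 6 and 12 months, because later attendance is selective and no rule handles it

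*Combined protocol and SAP*

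**What the plan says.** Section B.7.5 lists, as additional data, a "Comparison of mean change from Baseline in upper limb pain mean VAS score evaluated at 1, 3, 6 & 12months after device activation". The Revision History shows that the 6-month and 12-month visits were each added by amendment.

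Several passages bear on who is measured late:

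- Section B.6.14: "Subjects will be offered an optional visit at 12 months after device activation".
- Section B.6.13 (repeated in B.6.18): "all subjects who remain implanted at the time of Study Completion will be offered to return for an additional visit 12-months after device activation". Section B.6.19 attaches the same condition to the 6-month visit.
- Table 1, note c: "Some subjects were originally consented to complete the study at the 3 or 6 month visit and may not consent for additional visit". Note b adds that some subjects may have to be re-consented.
- Section B.6.15: under remote data collection, subjects who do not charge the device or who switch it off are not to be mailed questionnaires until they comply.

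On medication, subjects agree to study requirements "including not increasing pain medications through the three months visit" (B.3.2); B.6.4 and B.6.15 use the same end point.

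On analysis, B.9.2 states: "There are no formal hypotheses evaluated in this study. All baseline and outcome data will be reported using summary statistical methods". It adds: "Continuous variables will be summarized using means, standard deviations, and ranges". The only analysis population (B.7.1) is implanted subjects who complete the study without major deviations. B.6.12 and B.6.19 place completion at 3 months; B.6.18 expects visits through 12 months. No section gives a missing-data rule, a common cohort for the visit comparison, or per-visit denominators.

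**The concern.** A row of means at 1, 3, 6 and 12 months will be read as the course of pain in the implanted group. That reading needs the same subjects at each visit, or later losses that are unrelated to relief. The natural reasons for loss here (explant, switching off, withdrawal for poor effect, declining an extra visit) tend to remove subjects with little relief. The 12-month mean would then describe those who did well enough to return. Set beside a 3-month mean from nearly everyone, it mixes change over time with change in who is measured.

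Medication works in the same direction. The limit on increases ends at month 3, so a later VAS score may partly reflect added analgesics.

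At stake is the durability statement: a table can show steady relief while relief is fading.

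**Working it through.** **Inputs.** The documents give about 45 implanted subjects (B.5.4.1: "It is believed that approximately 45 subjects permanently implanted subjects will be sufficient"). They give no SD, correlation between visits, expected effect or retention, so there is no planned figure to reproduce. Everything below other than 45 is an assumption, shown as a range.

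**Step 1: exact identity.** For any visit, with both means taken as relief:

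bias of the observed mean = (1 − n seen / 45) × (mean relief in those seen − mean relief in those not seen)

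| Gap in relief, seen minus not seen | 36 of 45 seen (factor 1 − 36/45 = 0.20) | 27 of 45 seen (factor 1 − 27/45 = 0.40) |
|---|---|---|
| −1 cm | −0.20 cm | −0.40 cm |
| 0 | 0 | 0 |
| 1 cm | 0.20 cm | 0.40 cm |
| 2 cm | 0.40 cm | 0.80 cm |
| 3 cm | 0.60 cm | 1.20 cm |

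Positive values overstate relief. The direction rests entirely on the sign of the gap.

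**Step 2: how much of a loss can be hidden.** Assume:

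- a mean change of −4.00 cm at 3 months and a true loss of 0.50 cm, so −3.50 cm at 12 months;
- SD 2.3 cm at 3 months and 2.3-2.6 cm at 12 months, with correlation 0.5-0.7;
- 70% attending, with odds of attending doubling per SD of relief averaged over the two visits.

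The simulated 12-month mean of attenders is −3.88 to −3.96 cm.

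- Overstatement: 3.88 − 3.50 = 0.38 cm, to 3.96 − 3.50 = 0.46 cm.
- Loss shown in the table: 4.00 − 3.88 = 0.12 cm, to 4.00 − 3.96 = 0.04 cm.
- Share of the 0.50 cm loss hidden: 0.38/0.50 = 76%, to 0.46/0.50 = 92%.

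Over 55-70% attending, odds ratios of 1.5-2, and attendance driven by 3-month relief, 12-month relief or their average, the overstatement is about 0.1-0.7 cm.

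**Step 3: the two readings of completion.** A second simulation assumes SD 2.5 cm and correlation 0.7. Attendance depends on relief at the previous visit (log-odds 0.7 per SD, an odds ratio of about 2), with 90% seen at 6 months and 60% at 12.

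| Mean change (cm) | Month 1 | Month 3 | Month 6 | Month 12 |
|---|---|---|---|---|
| Truth | −4.50 | −4.50 | −4.00 | −3.50 |
| Available cases (completion at 3 months) | −4.50 | −4.51 | −4.12 | −3.97 |
| 12-month completers (completion at 12 months) | −4.98 | −5.03 | −4.63 | −3.97 |

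The true loss from month 3 to month 12 is 4.50 − 3.50 = 1.00 cm. Available cases show 4.51 − 3.97 = 0.54 cm. Completers show 5.03 − 3.97 = 1.06 cm, so the trend is nearly right, but the level is too favourable by 0.53 cm at month 3 (5.03 − 4.50) and 0.47 cm at month 12 (3.97 − 3.50).

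With much stronger selection (log-odds 1.4; 80% seen at 6 months, 50% at 12), available cases read −4.50, −4.51, −4.38, −4.48, and the fading almost vanishes.

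**Step 4: what a same-subject comparison achieves.** Using the Step 2 inputs with 55-70% attending and odds ratios of 1.5-2, the bias left in the same-subject change depends on what drives attendance:

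- 12-month relief: fading is still hidden by 0.08-0.41 cm.
- 3-month relief: fading is exaggerated by 0.06-0.33 cm.
- The average of both, with equal SDs: zero by symmetry.

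The remaining trend bias therefore runs from about −0.3 to +0.4 cm (positive meaning that fading is hidden).

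**The case against.** **Direction is not proven.** A reader might infer that lasting relief will be overstated. The documents do not establish this. Bias needs attendance to depend on relief, and no section shows that it does. Some loss is administrative: certain subjects consented only to 3 or 6 months. The stated durations suggest more. With 14 months of commitment inside a 26-month study, subjects would need to enrol by month 12 of a 20-month enrolment period; under uniform accrual that is 12/20 = 60%, or 27 of 45. Such loss need not bias the mean. If poorer responders return more often, relief is understated. This stands, and it is why the claim is limited to likely.

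**The text on 12-month follow-up is mixed.** The Synopsis, A.4 and B.5.5 say implanted subjects are followed for 12 months, and B.6.18 expects it. Table 1 marks the 12-month VAS as not optional. The Synopsis, A.4, B.5.5 and B.6.1 also offer the visit to current subjects and those past 6 months without restating the still-implanted condition. A reader might infer that the visit is strictly confined to those still implanted; that rests on B.6.13 and B.6.18 only. This limits how firmly the selection can be stated but does not remove it.

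**The group may not shrink.** If completion means 12 months, B.7.1 fixes the cohort. That is correct, but the error then moves from the trend to the level, as Step 3 shows.

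**Medication is partly controlled.** Use is recorded at every visit. Telephone reminders ask subjects not to change it before visits (B.6.10), and B.6.15 asks for stable dosing in the two weeks before follow-up visits. None of these extends the limit on increases beyond month 3.

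**Stakes are modest.** This is descriptive additional data with no hypothesis, so no test or error rate is affected. A reader might extend the point to the 3-month primary and secondary endpoints; the optional visits do not reach them. Nor do the documents state why the 12-month visit was added, so a purpose of proving durability is inference.

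**Conclusion.** The concern holds in limited form. Followed as written, the comparison is likely to make relief at 6 and 12 months look more lasting than it is, and nothing in B.7.5 or B.9.2 would reveal it. Under the stated assumptions the overstatement at 12 months is about 0.1-0.7 cm, enough to hide much of a 0.5 cm loss; it is zero if attendance is unrelated to relief. The form of the error depends on which definition of completion applies.

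Two stronger readings should be avoided. One is that the loss would vanish from the table: in the 0.5 cm case above, 0.04-0.12 cm still shows. The other is that a same-subject comparison cures the problem: it addresses the trend but not the level, and can leave a trend bias of either sign. The change should be made, but the study's main conclusion at 3 months does not hang on it.

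**What to change.** In B.7.5 and B.9.2:

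1. Show the 1-, 3- and 6-month mean change for exactly those seen at 12 months, beside the all-available means, with n at each visit.
2. Tabulate 3-month VAS change and responder status for 12-month attenders and non-attenders. This shows directly whether loss was related to earlier relief.
3. Give counts at each visit of subjects implanted, explanted, re-consented and assessed, with reasons for non-attendance that separate administrative from effect-related loss.
4. Show the share of subjects above baseline pain medication at each visit.
5. Label 6- and 12-month results as conditional on attendance, since item 1 does not correct the level and may leave some bias in the trend.

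Define completion once, reconciling B.6.12, B.6.18, B.6.19 and B.7.1.

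VAS and medication use are already scheduled at every follow-up visit in Table 1, so the cost is a few extra tables and a short wording change. No visit or procedure changes.

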#### **B.6.4. BASELINE**

A subject that is eligible to continue into the trial phase according to the inclusion and exclusion criteria will be requested to fill out standard questionnaires that will assess extent of disability and use of medications. The medical and surgical history of the subject will also be collected. At this visit and subsequent visits, the subject will be assessed for study-related adverse events, medication usage and will be reminded to not increase pain medications from baseline through the 3-Month Visit. Pre-operative assessments will follow the standard of care for SCS therapy and be determined by the site Investigator.

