### **B.6.10. TELEPHONE CALLS**

Subjects will be contacted by the study coordinator, via a telephone call, before each study visit. The study coordinator will check on the well-being of the subject, remind the subject of the upcoming scheduled visit, remind the subject not to change pain medication usage prior to the scheduled visit, and remind the subject to contact the Investigator/study staff should he/she have any concerns or questions. The telephone calls should be made two to three weeks *before* the scheduled visit.

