#### **B.6.15 OTHER ASSESSMENTS AND INFORMATION**

At any time during the study, if lead migration is suspected, the subject may have additional AP and lateral X-rays taken to confirm the new lead position in order to aid the Investigator in determining a course of action.

Paresthesia testing may also be performed to assess lead location and therapy coverage of pain areas. Programming adjustments may be made based on patient feedback following assessment.

Additional information on Medication Usage:

- The Investigator will instruct all subjects to take the Baseline doses of pain medication until the 3-Month Visit. However, after Device Activation Visit, the Investigator may reduce the dose of pain medication if the subject is benefitting greatly from DTM SCS therapy and not benefitting from Baseline dose pain medication.
  - Subjects should not fluctuate medication usage nor dosages even if the dose is at or below Baseline doses. The Investigator/Study staff will instruct all subjects to maintain stable dosing of medication for at least two weeks prior to scheduled follow-up visits.
- Following trial and permanent implants, the clinical site's standard practice for prophylactic pre-surgery antibiotics and post-surgery pain medications will be followed. Investigators/Study staff will instruct subjects not to change usage of any other concomitant pain medications.

Remote data collection from the subjects is allowed. This should be evaluated on a case by case basis, pending Investigator's approval based on safety and clinical condition. Subjects who are not demonstrating study compliance, e.g. not returning phone calls, not charging device or turning the device off should not be mailed study questionnaires until they demonstrate compliance with the study. The site should continue to contact the subject and ensure compliance before mailing the questionnaires. The communications will be documented in the source worksheets. Remote visits would apply to any visit that could be conducted remotely without the subject being present, including remote programming, if available. Procedural visits (trial and IPG) and any unscheduled visits required for study-related adverse events would continue to be performed in office where possible.

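### The dated limit on pain-medication increases stops at month 3, but VAS change from Baseline is compared through month 12 without reference to medication, so the 6- and 12-month results could mix DTM relief with medication effects

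*Combined protocol and SAP*

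**What the plan says.** **Limits dated to month 3.** Inclusion criterion 8 (B.3.2, repeated in the Synopsis) asks for willingness to meet study requirements, "including not increasing pain medications through the three months visit". B.6.4 says that at this and later visits the subject "will be reminded to not increase pain medications from baseline through the 3-Month Visit". B.6.15 adds: "The Investigator will instruct all subjects to take the Baseline doses of pain medication until the 3-Month Visit". The same section permits reductions after Device Activation: "the Investigator may reduce the dose of pain medication if the subject is benefitting greatly from DTM SCS therapy", on condition that the Baseline dose is not itself helping.

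**Instructions without their own month-3 date.** B.6.15 asks subjects to "maintain stable dosing of medication for at least two weeks prior to scheduled follow-up visits". B.6.10 has the coordinator call two to three weeks before each visit and "remind the subject not to change pain medication usage prior to the scheduled visit". B.6.15 also contains a sub-bullet against fluctuating usage or dosage, nested under the month-3 instruction, and a sentence against changing other concomitant pain medicines, placed in a bullet about the trial and permanent implants.

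**Effectiveness after month 3.** The Revision History shows that the 6-month visit came with revision 2.0 and the 12-month visit with revision 3.0. B.7.5 lists "Comparison of mean change from Baseline in upper limb pain mean VAS score evaluated at 1, 3, 6 & 12months after device activation", and B.8.1 names VAS at the same months among its effectiveness tests.

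**Use of medication data.** Table 1 records medication use at every visit, and B.6.1 lists it as assessed through month 12. B.7.3 to B.7.5 and B.8.1 do not mention it. B.9.2 plans descriptive summaries of baseline and outcome data and gives no rule for a subject whose medication has changed.

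**The concern.** The study is single-arm and open-label, so no comparator absorbs a change in co-treatment. The plan itself treats pain medication as a possible confounder: it requires a stable regime for 30 days before enrolment, and it excludes subjects whose medication for other conditions could disturb the endpoints. That protection was written around a 3-month endpoint. When the visits at 6 and 12 months were added, the dated limits were not extended to them.

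The B.7.5 comparison therefore sets months 1 and 3, read under an instruction not to exceed Baseline medication, beside months 6 and 12, where no such instruction clearly applies. If relief from stimulation fell after month 3 and medication rose in response, the mean VAS change would look better than stimulation alone had achieved. If subjects did well and cut their medication, it would look worse. The 6- and 12-month readings are the only data the study will have on whether relief lasts, so what is at stake is how far a statement of sustained relief can rest on them.

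**Working it through.** The plan gives no figure to reproduce: no hypothesis, effect size or SD lies behind the planned 45 or so implanted subjects, and no rate of medication change is stated. The check is of the text, followed by an illustration of scale.

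**Step 1. Passages set against the visits.**

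| Instruction | Months 1 and 3 | Months 6 and 12 |
|---|---|---|
| No increase (B.3.2, B.6.4) | applies | not stated |
| Baseline doses, reductions possible (B.6.15) | applies | not stated |
| Two-week stability before visits (B.6.15) | applies | appears to apply |
| Pre-visit reminder call (B.6.10) | applies | applies |
| No fluctuation; other pain medicines unchanged (B.6.15) | applies, the second in a peri-implant setting | unclear |
| VAS change from Baseline (B.7.5, B.8.1) | yes | yes |
| Medication use recorded (Table 1) | yes | yes |

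**Step 2. Do the undated instructions close the gap?** Take a dose raised above Baseline at month 4 and then held. It is stable for the two weeks before the 6-month visit, and it is unchanged after the reminder call. Both instructions are met with the dose above Baseline. B.6.9 also expects medication changes to be assessed at unscheduled visits at any time. The remaining two instructions might forbid such a rise, but their placement leaves that open.

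**Step 3. Scale (all inputs assumed).** Let f be the share of subjects above Baseline medication and d the VAS relief each gains from it. Shift in mean VAS change in favour of DTM = f × d.

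- Low: 0.10 × 0.5 cm = 0.05 cm
- Middle: 0.20 × 1.5 cm = 0.30 cm
- High: 0.40 × 2.0 cm = 0.80 cm
- No increases: 0 × d = 0

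**Step 4. Direction.** With reductions included, net shift = (f up × d up) − (f down × d down). If 10% increase and gain 1 cm while 30% reduce and lose 1 cm, the net is 0.10 − 0.30 = −0.20 cm, against DTM. The documents supply none of these four inputs, so the sign is not determined.

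**Step 5. Comparison with sampling error.** The 95% half-width of a mean with n = 45 is 1.96 × SD / √45. For assumed SDs of 2.0, 2.5 and 3.0 cm this is 0.58, 0.73 and 0.88 cm. The shift runs from negligible to about the size of sampling error. Unlike sampling error, it would not be reflected in a confidence interval.

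**Step 6. Group sizes for a split by dose.** 10% of 45 is 4.5 subjects and 40% is 18. The 12-month visit is optional (B.6.14), so the numbers there may be smaller.

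**The case against.** The case on the other side is substantial.

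- **Low stakes.** The primary endpoint and the VAS and disability secondary endpoints are read at month 3, inside the limit. The later VAS readings are additional data in a descriptive study with no hypothesis, and no durability objective is stated. This stands, and it confines the point to how the 6- and 12-month results are reported.
- **The text may already restrict later changes.** The two further B.6.15 instructions carry no end date of their own, so a reader who infers that nothing but the two-week rule survives month 3 goes too far. Their reach is unclear, which is a reason to reconcile the passages.
- **Nothing shows that doses rise.** A reader might infer that the 12-month result will be inflated, or that added medication will make fading relief look sustained. The documents do not support that. They contain no data on dosing after month 3, and they allow reductions. B.1 and C2 also describe this kind of pain as often poorly controlled by medication, so a gain of 1 to 2 cm is not assured. A shift of a few tenths of a centimetre could not hide a large loss of relief.
- **Medication may be tabulated anyway.** A reader might infer that any effect would be invisible in the output. B.9.2 covers baseline and outcome data in general terms and does not exclude a medication table. What is missing is a planned link between medication and VAS.
- **A split by dose is itself biased.** Dose after activation is a post-treatment variable, so subjects at or below Baseline are likely to be enriched for good responders. This stands and shapes the fix.

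**Conclusion.** The point holds as a gap in the reporting plan. The dated limit on increases ends at month 3, VAS effectiveness is evaluated through month 12, and the instructions that remain do not clearly keep doses at or below Baseline. As planned, the 6- and 12-month mean VAS changes cannot be attributed to DTM separately from changes in medication.

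The upward shift is 0.05 to 0.80 cm for f of 10% to 40% and d of 0.5 to 2.0 cm, and zero if no one increases. Those inputs are assumptions, and reductions could cancel or reverse the shift, so actual size and net direction are unknown. A reader might extend the concern to the 3-month responder rate. The documents do not support that, because that reading falls under the stated limit. This is a worthwhile, inexpensive improvement and does not challenge the study's main result.

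**What to change.** In B.7.5 and B.9.2, for months 6 and 12:

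1. Report the number of subjects whose pain medication is above, at or below Baseline, in the same table as the VAS change.
2. Add a supplementary descriptive proportion: among all analysed implanted subjects, those with at least 50% VAS relief and no increase in pain medication from Baseline. Show it beside any statement of sustained relief.
3. If VAS is also summarised by dose group, label it descriptive only, because dose is a post-treatment variable and the groups will be small.

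Separately, the sponsor should reconcile the medication text in B.3.2, B.6.4, B.6.10 and B.6.15 with the added visits, so that it is clear which instructions are meant to apply after month 3. No particular clinical rule is proposed here.

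The cost is a working definition of an increase, which the plan lacks and which must cope with different drug classes, plus a few lines of analysis text. No new data are needed. The sponsor should accept that the 6- and 12-month figure may come out less favourable.
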